### 8.2.1. Data Collection Principles

Patient data, including effectiveness, next line of therapy for the treatment of MDS, and survival status, will be collected from the date of initiation of AZA until 01 January 2021 or death, whichever is the earlier, as shown in [Table 8-2](#) below.

**Table 8-2. Definition of Data Collection End Date**

[figure not shown]
| Scenarios |   | Data Collection End Date  |
|-----------|---|---|
| A  | Patient remains on AZA throughout (beyond 01 January 2021)                | 01 January 2021   |
| B  | Patient has progression on AZA and AZA is discontinued                    | 30 days after discontinuation of AZA
(Data relating to survival and next treatment will be collected beyond this date.)                |
| C  | Patient discontinues AZA due to toxicity or investigator/patient decision | 30 days after discontinuation
(Data relating to date of progression, survival, and next treatment will be collected beyond this date.) |
| D  | Patient dies while receiving AZA  | Date of death   |
| E  | Patient is lost to follow-up  | Date of last available data   |

AZA azacitidine

In all scenarios, data collection starts on the date of AZA initiation.

The different scenarios for patient inclusion are shown in [Figure 8-1](#) below.

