#### 8.1.1. Primary Endpoint

**Complete Remission Rate** is defined as the proportion of patients who achieve a CR as documented within their EHRs, with confirmation of corresponding BM and peripheral blood parameters as defined per IWG 2006 MDS response criteria {Cheson 2006}, during the treatment period with AZA or prior to the initiation of next MDS treatment.

Definitions of responses categories are shown in [Table 8-1](#) below.

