### 8.1.2. Secondary Endpoints

**Real -World Complete Remission (rw-CR) Rate** is defined as the proportion of patients who achieve a CR as documented within their EHRs with or without confirmation of corresponding BM and peripheral blood parameters as defined per IWG 2006 MDS response criteria, during the treatment period with AZA or prior to the initiation of next MDS treatment.

**Objective Response Rate (ORR)** is defined as the proportion of patients who achieve a CR, or PR as documented within their EHRs with confirmation of corresponding BM and peripheral blood parameters as defined per IWG 2006 MDS response criteria, or achieve an mCR or HI, during the treatment period with AZA or prior to the initiation of next MDS treatment.

**Real -World Objective Response Rate (rw-ORR)** is defined as the proportion of patients who achieve a CR, or PR, as documented within their EHRs with or without confirmation of corresponding BM and peripheral blood parameters as defined per IWG 2006 MDS response criteria, or achieve an mCR or HI, during the treatment period with AZA or prior to the initiation of next MDS treatment.

**Duration of CR (DCR)** is defined as the interval from the first EHR documentation of a CR with confirmation of corresponding BM and peripheral blood parameters as defined per IWG 2006 MDS response criteria to the earlier of the first documentation of relapse, disease progression, or death from any cause.

**rw-DCR** is defined as the interval from the first EHR documentation of a CR with or without confirmation of corresponding BM and peripheral blood parameters as defined per IWG 2006 MDS response criteria to the earlier of the first documentation of relapse, disease progression, or death from any cause.

**Duration of Response (DOR)** is defined as the interval from when the criteria are first met for OR to the earlier of the first documentation of relapse, disease progression, or death from any cause.

**rw-DOR** is defined as the interval from when the criteria for rw-OR are first met to the earlier of the first documentation of relapse, disease progression, or death from any cause.

**Progression -Free Survival** is defined as the interval from the date of initiation of AZA to the earlier date of the first documentation of relapse, disease progression or death from any cause.

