| Dose Changes h   | 2     | Structured + Unstructured | X   | X            | X       | X         |                       |
| Dose Interruptions i   | 2     | Structured + Unstructured | X   | X            | X       | X         |                       |
| Discontinuation h  | 1&2   | Structured + Unstructured | X   | X            | X       | X         |                       |
| Reason for Treatment Discontinuation  | 1&2   | Unstructured              |   |              |         | X         | X                     |
| Data Related to Effectiveness  |       |                           |   |              |         |           |                       |
| Date of Response Assessment (From Progress Notes and/or Attachment for the Bone Marrow Report)                                | 1&2   | Unstructured              | X   | X            | X       | X         |                       |
| Response Category j (From Progress Notes and/or Attachment for the Bone Marrow Report)                             | 1&2   | Unstructured              | X   | X            | X       | X         |                       |
| IWG 2006 Response Assessment, Where Available k (From Progress Notes and/or Attachment for the Bone Marrow Report) | 1&2   | Unstructured              | X   | X            | X       | X         | X                     |
| If Progression, Date of Progression   | 1&2   | Unstructured              |   | X            | X       | X         | X                     |

| Data to be Provided if Available or Applicable                         | Stage | Source                            | Baseline (At AZA Initiation or Earlier as Applicable) | Study Period |         |           | Post-treatment Period |
|--|-------|-----------------------------------|---|--------------|---------|-----------|-----------------------|
|  |       |                                   |   | Visit 1      | Visit 2 | Visit (n) | Post-treatment        |
| Last USON Visit Date   | 2     | Structured + unstructured         |   | X            | X       | X         | X                     |
| Death Date   | 2     | Structured + LADMF + unstructured |   | X            | X       | X         | X                     |
| MDS Treatment After Discontinuation of AZA, if Applicable l | 1&2   | Structured + Unstructured         |   | X            | X       | X         | X                     |

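### Responses count until the next MDS treatment, but Table 8-2 closes collection 30 days after azacitidine without naming response or relapse, and Table 8-4 marks only some of the items needed later

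*Protocol*

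**What the plan says.** **Response window.** Section 8.1.1 counts a CR if it occurs "during the treatment period with AZA or prior to the initiation of next MDS treatment". Section 8.1.2 gives rw-CR, ORR and rw-ORR the same window; for the two objective response rates a patient may also qualify by marrow CR or haematologic improvement. No 30-day limit is stated anywhere in these definitions.

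**Collection period, text.** Section 8.2.1 says that patient data, with effectiveness named among them, "will be collected from the date of initiation of AZA until 01 January 2021 or death, whichever is the earlier, as shown in" Table 8-2.

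**Collection period, table.** Table 8-2 ends collection 30 days after azacitidine is stopped in Scenario B (progression) and Scenario C (toxicity, or investigator or patient decision). For B the exception is: "Data relating to survival and next treatment will be collected beyond this date". For C it is: "Data relating to date of progression, survival, and next treatment will be collected beyond this date".

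**Data items.** In Table 8-4 the post-treatment column is marked for IWG 2006 response assessment, marrow blasts, peripheral blasts, complete blood count and progression date. It is empty for "Date of Response Assessment (From Progress Notes and/or Attachment for the Bone Marrow Report)", for Response Category and for transfusion requirement. The table does not say how long the post-treatment period lasts.

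**Duration and PFS events.** DCR, rw-DCR, DOR and rw-DOR run "to the earlier of the first documentation of relapse, disease progression, or death from any cause", and PFS uses the same three events. Relapse is therefore an event in its own right, with its own criteria in Table 8-1.

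**The concern.** The endpoint definitions require information over a longer period than Table 8-2 collects it. The gap concerns patients who stop azacitidine, start nothing else and are followed for more than 30 days, which means chiefly Scenario C. An abstractor who follows the sentence in Section 8.2.1 and one who follows Table 8-2 would collect different data on the same patient.

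The study exists to isolate what magrolimab adds, and Section 8.7.4 says its results will be compared with single-arm Study 5F9005. A response lost to the collection rule can only lower the azacitidine rate, which favours the combination. Section 8.10 already warns that sparse marrow results will make CR and PR look too low; this would be an avoidable loss in the same direction. A lost relapse works the other way on the duration endpoints and PFS: it removes an event.

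**Working it through.** **1. The rules side by side**

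| Place | What it implies after azacitidine stops |
|---|---|
| 8.1.1, 8.1.2 | Responses count until next MDS treatment |
| 8.2.1, text | Effectiveness data to 01 January 2021 or death, with Table 8-2 as the detail |
| Table 8-2, B | 30 days, then survival and next treatment only |
| Table 8-2, C | 30 days, then progression date, survival and next treatment only |
| Table 8-4 | IWG response, blasts, blood count and progression date continue; response date, response category and transfusions do not; period undefined |

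**2. A response first documented after day 30, before next treatment**

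- *rw-CR or rw-PR.* Table 8-1 rests these on chart documentation, with or without the indices. The rows that hold such documentation are Response Category and Date of Response Assessment, and both are unmarked post-treatment. The IWG assessment row might pick up some cases, but only where an IWG-type assessment was recorded and only if that row continues past day 30. Capture is not assured.
- *IWG CR or PR.* Chart documentation is the first required element, so that element is lost. The remaining route is adjudication of cases whose blood and marrow indices qualify without documentation. Table 8-4 marks those indices post-treatment; Table 8-2 does not list them after day 30. Whether the route is open depends on which table governs.

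**3. A relapse after day 30 in a Scenario C responder**

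| Relapse criterion (Table 8-1) | Also a progression criterion? | Input marked post-treatment in Table 8-4? |
|---|---|---|
| Granulocytes or platelets down by at least 50% | Yes, same threshold | Yes |
| Hb down by at least 1.5 g/dL | Only from 2 g/dL | Yes |
| Marrow blasts back at pretreatment level | Not necessarily | Yes |
| Transfusion dependence | Yes | No |

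The exposed relapses are Hb falls of 1.5 to below 2 g/dL, some returns to pretreatment blasts, and those resting on transfusion dependence. A hypothetical blast example: pretreatment 4%, best response 2%, back to 4%. That is a relapse, but 4% does not exceed the 5% that the lowest progression band requires. In Scenario B progression has already happened, so the event is known and nothing is lost for these endpoints.

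**4. Size**

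The protocol gives no count of late responses. Its only relevant figures are the exact intervals of Table 8-5. With *x* responders in *n*, the Clopper-Pearson limits are Beta⁻¹(0.025; *x*, *n*−*x*+1) and Beta⁻¹(0.975; *x*+1, *n*−*x*). For *n* = 400 and *x* = 20, 40, 60, 80, 100 these give 3.1–7.6%, 7.2–13.4%, 11.6–18.9%, 16.2–24.3% and 20.8–29.5%, which reproduces the 400-patient column.

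Assume that a share *f* of true CRs first appears after collection stops and is missed. Then the observed rate is *p*(1−*f*). For *p* = 15% and *f* = 5%: 60 × 0.95 = 57, and 57/400 = 14.25%. Cells show the CRs observed, the rate and the 95% interval:

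| True CR rate (n = 400) | *f* = 5% | *f* = 10% | *f* = 20% |
|---|---|---|---|
| 10% (40) | 38, 9.50% (6.8–12.8) | 36, 9.00% (6.4–12.2) | 32, 8.00% (5.5–11.1) |
| 15% (60) | 57, 14.25% (11.0–18.1) | 54, 13.50% (10.3–17.2) | 48, 12.00% (9.0–15.6) |
| 20% (80) | 76, 19.00% (15.3–23.2) | 72, 18.00% (14.4–22.1) | 64, 16.00% (12.5–20.0) |

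Both *f* and *p* are assumptions. The table shows the direction and scale of a possible loss, not an estimate.

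**The case against.** The best defence is that the protocol collects more than Table 8-2 suggests. Section 8.2.1 names effectiveness data to 01 January 2021. Table 8-4 marks IWG response, blasts, blood counts and progression date post-treatment. Table 8-1 provides adjudication for undocumented cases with qualifying indices. Table 8-2 covers the first 30 days off treatment in full, and with monthly cycles an assessment after the last cycle can fall inside that window. Most relapse criteria coincide with progression criteria, and progression dates are collected beyond day 30 in Scenario C. Finally, Section 8.10 says marrow biopsies are not routine apart from diagnosis and suspected progression, so a first IWG CR more than 30 days off azacitidine should be uncommon.

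All of this stands and limits the point. A reader might infer that response data simply stop at day 30, or that relapses off treatment are missed as a rule. The documents support neither. A reader might also infer arbitrary censoring at day 30, but censoring rules may sit in the SAP, which is not at hand.

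The defence does not remove the inconsistency. Section 8.2.1 defers to Table 8-2, and Table 8-2 omits response and relapse. The adjudication route needs indices that Table 8-2 may have stopped, and it does not supply the chart documentation on which rw-CR and rw-PR depend. The transfusion row is unmarked under any reading.

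**Conclusion.** The protocol is inconsistent as written, and the inconsistency affects what is abstracted. It bears most directly on rw-CR and rw-PR (and so on rw-ORR) documented after day 30. It bears conditionally on late IWG CR and PR, and on a limited set of relapses in Scenario C responders that feed DCR, rw-DCR, DOR, rw-DOR and PFS.

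Any loss of responses can only push the azacitidine rates down. Its size cannot be derived from the document; the illustration assumes 5% to 20% of CRs missed and moves a 15% rate by 0.75 to 3 percentage points. It would be tempting to conclude that the primary CR count is demonstrably too low. That does not follow: the adjudication route and the marked Table 8-4 rows may capture late IWG CRs, and few may occur.

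**What to change.** Reconcile Sections 8.1.1, 8.1.2 and 8.2.1 with Tables 8-2 and 8-4 before Stage 2 abstraction:

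- State one response-ascertainment end date: the earliest of next MDS treatment, 01 January 2021, death or last available data.
- In Table 8-2, name response among the data collected beyond day 30 in Scenarios B and C. Name relapse as well for Scenario C responders, on the same terms as progression date. Scenario B needs no added relapse capture.
- In Table 8-4, mark Date of Response Assessment, Response Category and transfusion requirement in the post-treatment column, and define how long that column runs.

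The cost is edits to the text and two tables, matching eCRF changes, and a few more fields to abstract. Blood counts are structured data, and the Scenario C charts are already to be reviewed for progression and next therapy.

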**Figure 8-1 Scenarios for Patient Inclusion**

AZA azacitidine; Q1 first quartile; US United States

### 8.2.2. Eligibility Criteria

Study population will be identified by first applying inclusion/exclusion criteria in structured data in Stage 1. Then in Stage 2, additional inclusion/exclusion criteria of data only available through charts will be applied to further screen patients. Patients who meet all criteria from both stages will be the final study sample.

For the identification of about 20 patients for pilot chart review, some (but not all) of the additional inclusion/exclusion criteria of data only available through charts will be applied.

**Table 8-3. Eligibility Criteria**

|   | Stage 1
Criteria
applied
during
structured
data
extraction | Stage 1
Criteria to
confirm during
pilot chart
review
(Approximately
20 patients) | Stage 2
Criteria to
confirm
during full
chart review
(full sample) |
|---|---|--|---|
| Inclusion Criteria   |   |  |   |
| Patients must meet all the following inclusion criteria to be eligible:   |   |  |   |
| 1) Male or female $\geq 18$ years of age  | X   |  |   |
| 2) Documented histological diagnosis of MDS defined as per medical record documentation in the EHR  | X   | X  | X   |
| 3) Documented IPSS-R MDS risk category of intermediate, high, or very high risk   | X   | X  | X   |
| 4) Initiation of AZA monotherapy during the Study Index Period  | X   | X  | X   |
| 5) Received at least a single dose of treatment with AZA in line with US Prescribing information; the following dosing regimens are permitted:
a) AZA 75 mg/m  Days 1-7 of a monthly cycle
b) AZA 75 mg/m  Days 1-5, 8-9 of a monthly cycle (5 days on, 2 days off on the weekend, 2 days on)
c) AZA 75 mg/m  Days 1-5 of a monthly cycle  | X   | X  | X   |
| 6) Patients should not have received any anti-leukemic therapies for the treatment of MDS prior to the initiation of AZA. (Prior and concurrent therapy with hydroxyurea, oral etoposide, erythroid and/or myeloid growth factors, or any symptomatic treatment is allowed. Patients with MDS who received prior anti-cancer therapy from prior malignancies are permitted.)  | X   |  | X   |
| 7) Patients must have at least 1 posttreatment encounter in the EHR.  | X   |  |   |
| 8) WBC count $\leq 20 \times 10^3/\mu\text{L}$ at the time of AZA initiation (use of hydroxyurea to reduce WBC prior to AZA initiation, as documented within the EHR is acceptable).  | X   |  |   |
| 9) Adequate hepatic and renal function at the time of AZA initiation (within 30 days of index) as evidenced by the following documentation in the EHR:
a) AST and ALT $\leq 5 \times$ upper limit of normal (ULN)
b) Bilirubin $\leq 1.5 \times$ ULN, or $3.0 \times$ ULN and primarily unconjugated if patient has a documented history of Gilbert's syndrome or genetic equivalent
c) Serum creatinine $\leq 1.5 \times$ ULN or calculated glomerular filtration rate (GFR) $\geq 40$ mL/min/1.73 m  | X   |  |   |

|  | Stage 1
Criteria
applied
during
structured
data
extraction | Stage 1
Criteria to
confirm during
pilot chart
review
(Approximately
20 patients) | Stage 2
Criteria to
confirm
during full
chart review
(full sample) |
|--|---|--|---|
| Exclusion Criteria  |   |  |   |
| 1) Any prior anti-leukemic therapy including chemotherapy (excluding hydroxyurea or oral etoposide), targeted therapies, immunotherapy or radiotherapy   | X   | X  | X   |
| 2) Prior treatment with hypomethylating agents and/or low dose cytarabine. Prior treatment with lenalidomide or similar agents is permitted if treatment is utilized for symptomatic support (ie, anemia, RBC transfusion dependence). | X   | X  | X   |
| 3) Patients participated in an interventional clinical trial during study observation period.  | X   | X  | X   |
| 4) Previous hematopoietic stem cell transplant within 6 months prior to initiation of AZA, active GVHD, or requiring transplant-related immunosuppression.   | X   | X  | X   |
| 5) Patients who have had transformation of MDS into AML prior to initiation of AZA   | X   | X  | X   |
| 6) Known inherited or acquired bleeding disorders  |   |  | X   |
| 7) EHR documentation of clinical suspicion/ radiological evidence of active CNS involvement by leukemia  |   |  | X   |
| 8) Acute promyelocytic leukemia  | X   |  | X   |
| 9) Second malignancy, except treated basal cell or localized squamous skin carcinomas, localized prostate cancer, or other malignancies for which patients are not on active anti-cancer therapy as defined in Exclusion Criterion 1   | X   |  | X   |
| 10) Patients who initiated AZA treatment outside the approved label (except as described under the Inclusion Criterion 5) for example, in combination with other agents for the treatment of MDS                                       |   |  | X   |

AML acute myeloid leukemia; ALT alanine aminotransferase; AST aspartate aminotransferase; AZA azacitidine; CNS central nervous system; ECOG Eastern Cooperative Oncology Group; EHR electronic health record; GVHD graft versus host disease; IPSS R Revised International Prognostic Scoring System; MDS myelodysplastic syndrome; RBC red blood cell; ULN upper limit of normal; US United States; WBC white blood cell

### 8.3. Variables

The variables to be collected are listed below in

**Table 8-4.** In this table, unstructured data refer to medical data including text-based descriptions in physician notes that were recorded during routine patient care. In addition, please see Section 8.2.1, Principles of Data Collection for guidance regarding timing (start and end time) of data collection for the study and for individual patients.

**Table 8-4. Data Items and Timing for Surveillance**

| Data to be Provided if Available or Applicable  | Stage | Source       | Baseline (At AZA Initiation or Earlier as Applicable) | Study Period |         |           | Post-treatment Period |
|---|-------|--------------|---|--------------|---------|-----------|-----------------------|
|   |       |              |   | Visit 1      | Visit 2 | Visit (n) | Post-treatment        |
| Review of Eligibility Criteria  | 1&2   |              | X   |              |         |           |                       |
| Patient Demographics 
 
• Age at AZA initiation
 
• Race
 
• Sex
 
• Height and weight
 
• Geographical location of clinic
 
   | 1&2   | Structured   | X   |              |         |           |                       |
| Patient Demographics (Ethnicity)  | 2     | Unstructured | X   |              |         |           |                       |
| Clinical and Disease Characteristics   |       |              |   |              |         |           |                       |
| MDS Diagnosis Date  | 1&2   | Structured   | X   |              |         |           |                       |
| MDS Classification 
 
• RS and Single/Multilineage Dysplasia
 
• Multilineage dysplasia
 
• RS with multilineage dysplasia
 
• Excess blasts
 
• Isolated del 5q
 
• Unclassifiable/unknown/missing
 
 | 1&2   | Structured   | X   |              |         |           |                       |
| Therapy-Related or Secondary MDS (Yes/No/unknown)   | 1&2   | Unstructured | X   |              |         |           |                       |
| Date of AZA Initiation  | 1&2   | Structured   | X   |              |         |           |                       |
| Documented IPSS-R Risk Category a  | 1&2   | Structured   | X   |              |         |           |                       |
| Documented Cytogenetic Subgroup   | 1&2   | Unstructured | X   |              |         |           |                       |
| Documented Cytogenetics (Specify – Normal, del 11q, del 5q, del 12p, del 20q, etc)  | 2     | Unstructured | X   |              |         |           |                       |
| Documented TP53 Mutation  | 2     | Unstructured | X   | X            | X       | X         |                       |
| BM Blasts % at MDS Diagnosis  | 1&2   | Unstructured | X   |              |         |           |                       |
| BM Blasts % at AZA Initiation   | 1&2   | Unstructured | X   |              |         |           |                       |
| BM Blasts During Treatment  | 1&2   | Unstructured |   | X            | X       | X         | X                     |
| Peripheral Blasts During Treatment  | 1&2   | Unstructured |   | X            | X       | X         | X                     |

| Data to be Provided if Available or Applicable  | Stage | Source                    | Baseline (At AZA Initiation or Earlier as Applicable) | Study Period |         |           | Post-treatment Period |
|---|-------|---------------------------|---|--------------|---------|-----------|-----------------------|
|   |       |                           |   | Visit 1      | Visit 2 | Visit (n) | Post-treatment        |
| Requirement for Blood Transfusion (record units and frequency)  | 2     | Unstructured              | X   | X            | X       | X         |                       |
| ECOG/Karnofsky Performance Status/  | 1&2   | Structured                | X   | X            | X       | X         |                       |
| Comorbidity b  | 1&2   | Structured                | X   |              |         |           |                       |
| Prior Treatment for MDS Including Supportive Care c  | 1&2   | Structured + Unstructured | X   |              |         |           |                       |
| Information Collected at Baseline and During the Study   |       |                           |   |              |         |           |                       |
| Concomitant Medications   | 1&2   | Structured + Unstructured | X   | X            | X       | X         | X                     |
| Complete Blood Count d   | 1&2   | Structured                | X   | X            | X       | X         | X                     |
| Serum Chemistry e  | 1&2   | Structured f   | X   | X            | X       | X         | X                     |
| Liver Function Tests g   | 2     | Structured                | X   | X            | X       | X         | X                     |
| AZA Treatment-Related Data   |       |                           |   |              |         |           |                       |
| Dose Changes h   | 2     | Structured + Unstructured | X   | X            | X       | X         |                       |
| Dose Interruptions i   | 2     | Structured + Unstructured | X   | X            | X       | X         |                       |
| Discontinuation h  | 1&2   | Structured + Unstructured | X   | X            | X       | X         |                       |
| Reason for Treatment Discontinuation  | 1&2   | Unstructured              |   |              |         | X         | X                     |
| Data Related to Effectiveness  |       |                           |   |              |         |           |                       |
| Date of Response Assessment (From Progress Notes and/or Attachment for the Bone Marrow Report)                                | 1&2   | Unstructured              | X   | X            | X       | X         |                       |
| Response Category j (From Progress Notes and/or Attachment for the Bone Marrow Report)                             | 1&2   | Unstructured              | X   | X            | X       | X         |                       |
| IWG 2006 Response Assessment, Where Available k (From Progress Notes and/or Attachment for the Bone Marrow Report) | 1&2   | Unstructured              | X   | X            | X       | X         | X                     |
| If Progression, Date of Progression   | 1&2   | Unstructured              |   | X            | X       | X         | X                     |

| Data to be Provided if Available or Applicable                         | Stage | Source                            | Baseline (At AZA Initiation or Earlier as Applicable) | Study Period |         |           | Post-treatment Period |
|--|-------|-----------------------------------|---|--------------|---------|-----------|-----------------------|
|  |       |                                   |   | Visit 1      | Visit 2 | Visit (n) | Post-treatment        |
| Last USON Visit Date   | 2     | Structured + unstructured         |   | X            | X       | X         | X                     |
| Death Date   | 2     | Structured + LADMF + unstructured |   | X            | X       | X         | X                     |
| MDS Treatment After Discontinuation of AZA, if Applicable l | 1&2   | Structured + Unstructured         |   | X            | X       | X         | X                     |
| Hematopoietic Stem Cell Transplant                                     | 1&2   | Unstructured                      |   | X            | X       | X         | X                     |

AZA azacitidine; BM bone marrow; ECOG Eastern Cooperative Oncology Group; IPSS R Revised International Prognostic Scoring System; IWG International Working Group; LADMF Limited Access Death Master File; MDS myelodysplastic syndrome; RS ring sideroblasts; USON US Oncology Network

a At MDS diagnosis or at AZA initiation

b As per National Cancer Institute comorbidity index. c Record drugs used and start end dates.

d Complete blood count includes hemoglobin, erythrocyte count; total leukocytes, absolute neutrophil count, lymphocytes, monocytes, and platelet count.

e Serum chemistry includes sodium, potassium, urea, uric acid, creatinine, and lactate dehydrogenase.

f Except for lactate dehydrogenase which is captured from Unstructured data.

g Liver function tests include alanine aminotransferase, aspartate aminotransferase, alkaline phosphatase, gamma glutamyl transferase, total bilirubin, albumin, and total protein.

h Includes start and end dates and reason.

i Defined as stopping treatment permanently including date and reason for discontinuation.

j Response as documented within the electronic health record.

k Complete remission, partial remission, and stable disease including the assessment criteria used (eg, IWG 2006, IWG 2000, etc.).

l Drugs used and duration (start and end dates) this includes autologous/allogeneic hematopoietic stem cell transplant.

Due to privacy and compliance reasons, McKesson will be not be transferring the actual dates for any variables, including those for laboratory assessments and response assessments. A study day relative to the Index date for all variables including laboratory and response assessments will be transferred to Gilead Sciences in the final data set. Some additional data including month/year or “week of” dates could be shared after compliance review. Deidentified patient data will be provided; however, depending on the situation (small cell sizes or sensitive information like age > 90), some variables may be required to be aggregated or put into categories.

